### **11-12 DATA RETENTION**

The following documents will be archived in the CRNH of Auvergne to the end of the period of practical use (15 years).

These documents are:

- Protocol and appendix, any amendments,
- Information and consent forms signed (originals)
- Individual data (authenticated copies of raw data)
- Follow-up documents
- Statistical analysis

- Final report of the study

At the end of the period of practical use, all documents to be archived, will be under the responsibility of the INRA for 15 years after the end of the study according to institutional practices.

No destruction can be performed without the consent of the sponsor. At the end of the 15 years, the sponsor will be consulted for destruction. All data, all documents and reports may be subject to audit or inspection.

### **11-13 PUBLICATION POLICY**

Investigator will have full and unrestricted access to the database with all anonymized data. Anonymised data and outcomes of this study will be shared within partners of the FOOTBALL consortium (Appendix 7).

The outcomes of this study will be published in field relevant peer-reviewed journals thereby presenting the results to the scientific community. Other forms of communication include presentations at national and international meetings as well as media releases. Outcomes may be included in databases for dietary biomarkers created within the project FOOTBALL.

Rules for publications have been defined in the FOOTBALL consortium agreement.

## **13 - APPENDIX**

Appendix 1 : Signature page

Appendix 2 : Food Frequency Questionnaire

Appendix 3 : Nutritional Composition of Fresubin ® 2kcal fiber

Appendix 4 : Restricted diet for Day 1

Appendix 5 : Restricted diet for Day 2

Appendix 6: Composition of the standardized dinner for Days 2 and 3

Appendix 7: FOODBALL consortium

## **Appendix 2 : Dietary questionnaire**

Exemple of questions translated from original in French for the volunteers:

Breakfast

At what time, foods usually consumed with quantities ?

Standing or sitting?

Same every day or changing?

Do you eat snacks in the day?

At what time? At what frequency?

What food do you eat as snacks?

What do you drink?

Water: less than 0.5l per day or 0.5 to 1l per day, or 1 to 2l/day, or more?

Wine: no or 2-3 glasses per day, or 4-7 glasses per day, or more?

Beer or cider: no or 1 can or more?

Fruit juice: no or 1 glass per day or 2-3 glasses per day, more (how many)?

Sweetened beverages: no or 1 glass per day or 2-3 glasses per day, more (how many)?

What do you drink?

Raw vegetables: every meal or once a day or once a week

Cooked vegetables: every meal or once a day or once a week

Meat: every meal or once a day or less (how many?) or never

Fish: never, once a week, more (how many?)

Eggs: never, once a week, more (how many?)

### Appendix 3 : Nutritional Composition of Fresubin ® 2kcal fiber

Fresubin ® 2kcal fibre is a high energy nutritional supplement developed by Fresenius Kabi. It is composed mainly by protein milk, vegetables oils (rapeseed oil, sunflower oil), carbohydrates, vitamins, minerals and fibre. It is a lactose and gluten free product. Data available at: <http://www.fresenius-kabi.co.uk/4727.htm>

#### Energy and Macronutrient Composition

Nutritional Composition		Per 100ml	Per 200ml
Energy	kcal	200	400
Protein	g	10	20
Nitrogen	g	1.6	3.2
Carbohydrate	g	21.8	43.6
Of which sugars	g	3.3-6*	6.6-12*
Of which lactose	g	≤0.3	≤0.6
Fat	g	7.8	15.6
Of which saturated fatty acids	g	0.6	1.2
Of which polyunsaturated fatty acids	g	1.4	2.8
Of which monounsaturated fatty acids	g	5.8	11.6
Fibre	g	1.5	3
Water	ml	68	136
Osmolarity	mosmol/l	590-615	590-615

#### Micronutrient composition

Minerals and Trace Elements		Per 100ml	Per 200ml
Sodium	mg (mmol)	60 (2.6)	120 (5.2)
Potassium	mg (mmol)	160 (4.1)	320 (8.2)
Chloride	mg (mmol)	80 (2.3)	160 (4.6)
Calcium	mg (mmol)	205 (5.1)	410 (10.2)
Phosphorus	mg (mmol)	120 (3.8)	240 (7.6)
Magnesium	mg (mmol)	16 (0.66)	32 (1.32)
Iron	mg	2.5	5
Zinc	mg	1.6	3.2
Copper	µg	375	750
Manganese	mg	0.5	1
Iodide	µg	37.5	75
Chromium	µg	12.5	25
Molybdenum	µg	18.8	37.6
Fluoride	mg	0.25	0.5
Selenium	µg	13.5	27

Vitamine		Per 100ml	Per 200ml
Vitamin A	µg	150	300
Beta-carotene	µg	375	750
Vitamin D	µg	2.5	5
Vitamin E	mg	3.75	75
Vitamin K	µg	21	42
Vitamin B1	mg	0.3	0.6
Vitamin B2	mg	0.4	0.8
Nicotinamide	mg	3.75	7.5
Vitamin B6	mg	0.43	0.86
Vitamin B12	µg	0.75	1.5
Pantothenic Acid	mg	1.5	3
Biotin	µg	9.4	18.8
Folic Acid	µg	62.5	125
Vitamin C	mg	18.8	37.6

## **Appendix 4 : Restricted diet for Day 1**

No intake of tomato in any form : raw tomato or cooked tomato, tomato products (sauce, paste, ketchup) and dishes containing tomato (pizzas, soup, ratatouille, chili con carne...).

No intake of banana in any form.

No alcohol.

## **Appendix 5 : Restricted diet for Day 2**

No intake of tomato in any form : raw tomato or cooked tomato, tomato products (sauce, paste, ketchup) and dishes containing tomato (pizza, soup, ratatouille, chili con carne...).

No intake of banana in any form.

No intake of plant-based beverages : coffee, tea, herbal teas, chocolate, fruit juices, wine, beer.

No intake of fruits and vegetables, legumes, salad, breakfast cereals, wholegrain products.

No intake of soft drinks.

No alcohol

Animal products (meat, fish, eggs, etc...), dairy products (butter, cream, yogurt, cheese), pasta, white rice, potatoes, white bread are allowed.

Water and milk are the only beverages allowed.

## **Appendix 6: Composition of the standardized dinner for Days 2 and 3**

- The dinner will be prepared at home by the volunteers, using food bought in local grocery.
- The dinner will be composed of chicken breast simply pan-fried with butter or margarine, boiled white rice with salt, butter or margarine, and white bread.
- The volunteers can eat as much as they want.

Projet BioBanaTom “Identification of new biomarkers of banana and tomato intake”

Protocol ID: 2016-A00153-48

Statistical Analysis for urinary and plasma metabolome changes

after banana and tomato intake

Version 2 – 25/06/2018

The statistical analysis is centralized and performed by the INRA investigators, in close collaboration with the statistician of the Metabolomics platform ([name] INRA, [name], PFEM: Plateforme d’Exploration du Métabolisme).

The dataset resulting for, the urine samples of the clinical trial, ion intensities is normalized according to the volume collected for each urine fraction. A PCA model is applied to the normalized dataset to detect possible outliers in the dataset. Q primary PLSDA model is built using the three interventions as “Y” variables. The dataset are also assessed separately for banana versus control and tomato versus control.

To better discriminate the ions according to the intake of banana, an OSC-PLSDA model is built with the dataset containing control and banana samples (n=24). Statistical analysis is performed with SIMCA-P+ software (version 14.0, Umetrics, Umea, Sweden). The OSC filter is built with log transformed and Pareto scaled data using treatment (banana vs control; tomato vs control) as correction factor. A k-fold cross validation method is used with 4 subsets to predict the ability of the model to correctly classify samples to the corresponding dietary treatment. Q^2 is used to assess the prediction power and to determine the reliability of the model a permutation test (n= 500) is carried out.

Simultaneously, the difference in intensity of the extracted features between dietary treatments is assessed by applying a Student T test with Benjamini Hochberg correction (BH) for multiple comparisons using Metaboanalyst 3.0 [20]. Significance level is established at p value BH <0.05. Those features with a variable importance of projection (VIP) higher than 2 in the OSC-PLS-DA model, a T-test with BH p value <0.05 and which present in higher intensity in the urinary samples of the banana group are prioritized for identification as candidate biomarkers of banana intake. The same strategy is applied for the tomato dataset.

The dataset resulting from the analysis of plasma samples is assessed separately for banana and tomato versus control. Principal component analysis is performed for the detection of outliers in the dataset. For a first selection of ions, a one way ANOVA with a post hoc between the different time points is

applied using SPSS IBM version 22. Ions that were higher and significantly different than time point 00h (p value <0.01) are selected to be analyzed using a PLSDA model using SIMCA-P (version 14.0, Umetrics, Umea, Sweden). Ions with a VIP>2 and in higher intensity in banana or tomato are selected as plausible biomarkers of intake.

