Protocol description	Written consent will be obtained after complete information of the subjects about the objectives, and the nature and possible risks of the study (informed consent form in duplicate, one copy given to the volunteer). The protocol will be explained in details, with objectives and constraints, according to the information form, by the scientist in charge. A clinical exam and a check-up of all selection criteria will be performed by the main investigator or another medical doctor.  At the inclusion visit, subjects will have a medical exam including questionnaire

	
regarding past medical history, family background, medical treatments and standard clinical exam (weight, height, blood pressure) and a blood sampling. A food frequency questionnaire will also be completed. The conformity to the selection criteria will be checked during this medical exam. The selected subjects will be definitely included after validation of the selection criteria by the investigator.
 
The volunteers will consume in 3 distinct experimental periods either a control drink (oral nutritional complement Fresubin, 250 mL), or 240g banana (and 150 ml Fresubin), or 300g tomato (with 12 g sunflower oil and 150 mL Fresubin). Every volunteer will consume the 3 test foods, in a randomized order. After test food intake, urine will be collected over 24h in 7 fractions. Blood samplings will be performed before the food consumption (t0) and in post-prandial period (4 samplings at 1h, 2h, 4h et 6h), as well as on the following day in fasting state (t24h). the volunteers will follow a tomato and banana-free diet during the study days, as well as a more restrictive diet, without plant-based food, on the sampling days and on the day before. A 24h recall will be filled for the dietary intakes on the day before the sampling days (D2).
 
Samples will be analyzed using an untargeted metabolomics approach (LC-MS, GC-MS et RMN) with the aim to identify new biomarkers of tomato and banana intake.
 
The total volume of sampled blood will be 154 ml per subject.

Duration	
Duration of the study for every volunteer : 8 weeks
 
Total duration of the study: 6 months for the subject selection and realization of all experimental periods for all the volunteers
 
Total duration of the project : 3 years

Indemnities	350€ per subject

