### **4 – PROTOCOL DESCRIPTION**

The present project is a randomized, controlled, crossover study with 12 subjects. A cross-over design has been selected as each subject can serve as his/her own control thereby minimizing variations. Limitations attributed to cross-over designs are possible order or carry-over effects. These effects will however be minimized due to a randomized intervention order. The study design does not allow blinding as intervention is the ingestion of different foods.

In this study, we will assess the metabolomic profiles of human biofluids after consumption of two different foods: banana (240g peeled fruit) and tomato (300g fresh fruit) in order to identify novel biomarkers for each food. As a control diet, a high energy high protein drink, Fresubin ® 2kcal fiber (Fresinius kabi) will be used. As shown in the general study plan, the intervention comprises three dietary intervention periods of 4 days each for each food of interest and the control drink. Each

intervention period will be separated by a washout period of minimum 3 days (and maximum 10 days). Volunteers will be randomly assigned to a different food at each time point. Volunteers will be asked to maintain their normal physical activity and follow the dietary recommendations between intervention periods; they will receive an information form containing the description and objectives of the project, and detailed instructions. A volunteer’s booklet will also include simple information about nutritional metabolomics and a calendar marked with their visits to our facilities.

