## General study plan

In total 12 subjects (with the aim of 10 subjects completing the study) will be recruited for the present project of which 50% (n=6) will be men and 50% will be women (n=6) between 18 and 40 years of age. Subjects will have a BMI above 18.5 and under 30 kg/m^2, will be nonsmokers and with no disease diagnosis.

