## 9 – STATISTICAL ANALYSIS

Data will be collected in ad hoc developed databases and analyzed according to the classical workflow used for metabolomics data. Data will be cleaned in a standardized way. Univariate (ANOVA with Benjamini Hochberg correction) and multivariate analyses (Principal Component Analysis, Partial-Least-Square-Discriminant Analyses, and Hierarchical Clustering analysis) will be applied to pinpoint the detected metabolites which significantly vary along time after the intake of banana or tomato.

The statistical analysis will be centralized and performed by the INRA investigators, in close collaboration with the statistician of the Metabolomics platform ([name], PFEM: Plateforme d'Exploration du Métabolisme).

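### Urine candidates are selected by a two-food t-test with no stated pairing, so the third food never informs the error term; one three-food crossover model per ion would be a cheap improvement

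*SAP*

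**What the plan says.** The protocol is a three-period crossover: "Every volunteer will consume the 3 test foods, in a randomized order" (Summary). Section 4 gives the reason: "A cross-over design has been selected as each subject can serve as his/her own control thereby minimizing variations". The same section recognises possible order effects.

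For urine, the SAP first fits a multivariate model to all the data ("PLSDA model is built using the three interventions as" the response classes). It then splits the data: "The dataset are also assessed separately for banana versus control and tomato versus control". The size is given for banana: "an OSC-PLSDA model is built with the dataset containing control and banana samples (n=24"). Tomato follows the same strategy.

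An ion is prioritised if it passes three conditions together: VIP above 2 in the two-food model, a Student t-test with BH-adjusted p below 0.05, and higher intensity under the food. The SAP does not say whether the t-test is paired and names no volunteer or period term.

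Section 9 of the protocol lists "Univariate (ANOVA with Benjamini Hochberg correction") as the univariate method, also without naming model terms. Section 5-2 declines a power calculation and speaks only of thousands of metabolites.

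**The concern.** The t-test is one of the conditions that an ion must meet, so its power limits how many true markers can be found. Two features of the test as written can cost power.

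- **Pairing is not stated.** An unpaired test on 24 samples leaves between-volunteer variance in the error, which is what the crossover was chosen to remove.
- **The third food is left out of each error estimate.** This loss remains after pairing. The error variance of a banana-control comparison then rests on 12 differences only, although the tomato period of the same volunteers also carries information on within-volunteer variability.

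At an ordinary 5% level the second loss is minor. At the small p values that BH requires among thousands of ions, the critical t depends strongly on the error degrees of freedom (df). The three-intervention multivariate model does not make up for this, because it gives no p value per ion.

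**Working it through.** **Inputs from the documents.** 12 volunteers, 3 foods, 3 periods; 24 samples in the banana-control dataset; BH at 5%. The plan's own figure reproduces: 12 volunteers × 2 foods = 24, that is, one value per volunteer and food.

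**Assumptions, because the documents give no figures.** 2,000 ions; about 10 discoveries; two-sided tests; the six food orders used twice each; equal residual variance σ² on the log scale unless stated otherwise. The per-ion BH threshold is then 0.05 × 10/2000 = 0.00025. Effect size dz is the mean within-volunteer difference divided by the SD of the differences.

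**Degrees of freedom** (samples minus rank of the design matrix):

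| Model | Samples | Rank | Error df |
|---|---|---|---|
| Unpaired two-food t-test | 24 | 2 | 22 |
| Paired two-food t-test | 24 | 13 | 11 |
| Two foods, volunteer + period + food | 24 | 15 | 9 |
| Three foods, volunteer + food | 36 | 14 | 22 |
| Three foods, volunteer + period + food | 36 | 16 | 20 |

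Like for like, the comparison is 9 against 20 (period in both) or 11 against 22 (period in neither). I use 11 against 20 below because it compares a paired t-test with the model proposed; it is the smallest of these gaps.

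**Where the gain comes from.** In all four within-volunteer models the banana-control contrast has variance σ²/6. The gain is therefore only in error df. The non-centrality is dz × √12.

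**Power at p = 0.00025.** The critical t is 5.31 with 11 df and 4.44 with 20 df.

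| dz | Paired, 11 df | Three-food, 20 df |
|---|---|---|
| 1.2 | 25% | 43% |
| 1.5 | 51% | 75% |
| 1.8 | 76% | 93% |
| 2.0 | 88% | 98% |
| 2.5 | 99% | 100% |
| 3.0 | 100% | 100% |

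At a per-ion p of 0.05 and dz 1.0 the gap is only 88% against 91%. At p = 0.0001 and dz 1.5 it is 36% against 63%.

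**With the BH step simulated** (2,000 ions, 20 true markers, equal variances), the share of true markers found is 7% against 18% at dz 1.0, 60% against 84% at dz 1.5, 94% against 99% at dz 2.0, and 100% for both at dz 3.0. The false discovery proportion stayed between 3% and 7% for both methods.

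**If the test is unpaired.** By simulation at dz 1.5 and p = 0.00025, power is 77%, 52% and 27% for an assumed between-visit correlation of 0, 0.3 and 0.5. So the unpaired test matches the three-food model when visits are uncorrelated, is about level with the paired test at 0.3, and is much worse at 0.5.

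**With 10 completers.** The protocol plans "In total 12 subjects (with the aim of 10 subjects completing the study"). The df become 9 (paired) against 30 − (10 + 2 + 2) = 16. Power at dz 1.5 is about 30% against 54%; this is approximate, since 10 volunteers cannot fill six orders evenly.

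**Unequal variances** (simulation, p = 0.00025). For the banana-control test at dz 1.5, with the SD under tomato as a multiple of the SD under the other two foods:

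| Tomato SD | Paired | Pooled, 20 df |
|---|---|---|
| 1× | 51% | 75% |
| 1.5× | 51% | about 50% |
| 2× | 51% | 25% |
| 3× | 51% | 4% |

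For an ion with no mean difference but an SD under banana of 2× or 3×, the pooled test's type I error is about 0.0009 to 0.0010 or 0.0017 at nominal 0.00025. The paired test stays near nominal.

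**The case against.** The strongest case for the plan is that separate paired contrasts are a legitimate choice that is robust to unequal variance. Ions specific to one food are those whose variance may well differ between foods. Pooling over three foods can then cancel the gain (tomato SD 1.5×), reverse it (2×), or inflate type I error. This stands, and inspecting residual plots is not a realistic safeguard for thousands of ions. The power loss, however, falls mainly on ions that respond to the other food. Both problems can be met with food-specific variances, and a paired check on the selected ions exposes the inflation.

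The diet on the sampling day and the day before excludes banana, tomato and most other plant foods, so strong markers may have dz well above 2, where both tests succeed. This also stands: the loss concerns moderate markers. Selection also requires VIP above 2, so BH power is not the same as the yield of candidates.

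A reader might infer four stronger points that the documents do not support:

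- *The third period is thrown away.* It is not. All periods enter the three-intervention PLS-DA, and each food's periods enter its own test. The third food is absent only from the other food's error term.
- *Period cannot be separated from food in the two-food dataset.* Under balanced orders it can: that model has full rank, with 9 error df.
- *The SAP replaced a three-food ANOVA.* Section 9 of the protocol names ANOVA for change over time after intake, without volunteer or period terms, so this is not shown.
- *Plasma is affected in the same way.* The SAP does split plasma by food ("The dataset resulting from the analysis of plasma samples is assessed separately for banana and tomato versus control"), but it selects ions by ANOVA across time points at p below 0.01, then by PLS-DA. None of the figures here applies to that rule.

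**Conclusion.** The point holds for urine, as a cheap improvement and not as an error that invalidates the plan. The stated test uses neither a volunteer term nor the third food in its error estimate.

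That the test has 11 df is an inference and not something the SAP says. Read as written, a Student t-test on 24 samples has 22 df, and its weakness is then the between-volunteer variance left in the error. Only if it is paired does the comparison become 11 against 20 df, worth about 24 percentage points at dz 1.5 and 10 at dz 2.0, and almost nothing from 2.5 upward.

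These sizes rest on the assumed threshold, effect sizes, balanced orders and equal variances. The direction is firm when variances are similar across foods; it can reverse when one food's SD is 1.5 to 2 times the others.

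**What to change.** In the urine part of the SAP:

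1. For each ion, fit one linear model to log intensity with volunteer, period and food, using all volunteer-periods. Take the banana-control and tomato-control contrasts and apply BH to each contrast separately.
2. Deal with unequal variance explicitly. Either allow food-specific residual variances, which gives back part of the df gain, or report the paired two-food t-test as a sensitivity analysis for the selected ions. The second option reveals inflated type I error but does not recover ions missed through a pooled variance that is too large; the first addresses both.
3. If the two-food t-test is kept as the main test, state that it is paired.
4. Keep the two-food OSC-PLS-DA for VIP as planned.

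The cost is SAP wording, a short script and a little more analysis. No further samples or measurements are needed. The downside is the variance assumption, which step 2 addresses.

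### Urine OSC-PLS-DA: the SAP does not provide for refitting the treatment-based filter within folds and permutations, so the reported Q2 can be biased upward and the permutation test can reject too often

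*SAP*

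**What the plan says.** The SAP's urine analysis first plans an unfiltered model: "Q primary PLSDA model is built using the three interventions as" the Y variables. It adds: "The dataset are also assessed separately for banana versus control and tomato versus control", without naming a model for that step.

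For the pairwise comparison, "an OSC-PLSDA model is built with the dataset containing control and banana samples (n=24"). The filter is described next: "The OSC filter is built with log transformed and Pareto scaled data using treatment (banana vs control; tomato vs control) as correction factor". Validation follows: "A k-fold cross validation method is used with 4 subsets to predict the ability of the model to correctly classify samples", and then "Q^2 is used to assess the prediction power and to determine the reliability of the model a permutation test (n= 500) is carried out". For tomato, "The same strategy is applied for the tomato dataset".

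Candidates are chosen by a separate rule. It begins "Those features with a variable importance of projection (VIP) higher than 2 in the OSC-PLS-DA model" and adds a Benjamini-Hochberg t test below 0.05 and higher intensity in the food group. It contains no Q2 or permutation threshold.

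The SAP does not say whether the filter is refit in each fold or permutation. It also does not state the OSC algorithm or the numbers of OSC and PLS components. Protocol section 9 lists PCA, PLS-DA, hierarchical clustering and BH-corrected ANOVA, and does not mention OSC, cross-validation or permutation.

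**The concern.** OSC uses the treatment labels to decide which variation to remove. If it is fitted once to all 24 samples, the labels of the samples later held out have already shaped their own filtered data. Predicting those labels is then no longer an out-of-sample test.

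The permutation test has a related weakness under a further condition. If the filter stays tied to the true labels while only the PLS-DA labels are shuffled, the observed Q2 has an advantage that the permuted values lack.

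Q2 and the permutation test are the SAP's stated measures of prediction power and reliability, and it describes them only for the OSC model. If both are inflated, a reader cannot tell how much of a reported Q2 reflects food intake and how much reflects the filter.

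**Working it through.** **1. The plan's own figure.** 12 subjects (Protocol section 4) × 2 interventions = 24, which agrees with the SAP. With 4 subsets, 24 / 4 = 6 samples are held out at a time. If a subject's two samples stay together, that is 12 / 4 = 3 subjects per fold.

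**2. Mechanism.** Let y be the centred treatment label. Suppose a shared factor f drives many ions, so that X = f·l′ + E. Split f = a·y + g, with g orthogonal to y. With 24 samples, a is rarely exactly zero even when food has no effect. OSC removes g and leaves roughly a·y·l′ + E, so each sample, including those held out later, carries a scaled copy of its own label. If the filter is fitted on training samples only, the held-out label is not used. If ions are uncorrelated, there is no dominant f and little to leak.

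**3. Measure.** Q2 = 1 − Σ(yᵢ − ŷᵢ)² / Σ(yᵢ − ȳ)², with ŷᵢ predicted from the other folds. Without a food effect it should be at or below zero.

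**4. Simulation without a food effect.** The documents give no Q2 and only the word thousands for the number of metabolites (Protocol section 5-2), so these inputs are assumptions:
- 12 × 2 samples, 800 ions, within-subject correlation 0.5
- three latent factors carrying 60% of variance
- one-component PLS-DA, four folds of three subjects, 200 data sets per setting

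The last column is the share of data sets with permutation p ≤ 0.05 when the filter is fixed to the true labels. Ranges span free and within-subject permutation.

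| OSC setting | Median Q2, filter built once | Median Q2, refit in folds | Difference | p ≤ 0.05, filter fixed |
|---|---|---|---|---|
| Iterative, 1 component | −0.13 | −0.54 | 0.41 | 20.5–29% |
| Iterative, 2 | 0.15 | −0.67 | 0.82 | 58.5–63% |
| Iterative, 3 | 0.67 | −0.46 | 1.13 | 94–97% |
| Direct, 1 | −0.14 | −0.36 | 0.22 | 5.5–13% |
| Direct, 2 | −0.03 | −0.53 | 0.50 | 18–30% |
| Uncorrelated ions | −0.01 | −0.04 | 0.03 | 5% (iterative, 2) |

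With the filter refit for each permutation but still outside the folds, rejection was 3.5–7.5%; fully nested, it was 2.5–8%. The Monte Carlo standard error at 5% is √(0.05 × 0.95 / 200) ≈ 1.5 points.

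**5. Agreement.** Separately coded runs with iterative OSC and 1, 2 or 3 components gave −0.13, 0.15 and 0.68 built once, against −0.57, −0.60 and −0.37 nested. The differences are 0.44, 0.75 and 1.05. Another simulation (500 or 2000 features, within-subject correlation 0 or 0.5, two OSC types) showed an upward shift in mean Q2 of 0.19 to 0.56 in all 24 settings. Classification accuracy was 58–84% built once and 51–54% nested. In its permutation runs (300 or 500 features), fixed-filter rejection was about 14–80%, and about 3–13% when the filter was refit for each permutation.

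**6. With a real effect.** The Q2 columns use iterative OSC with 2 components, on the assumptions of step 4. The last column is the median difference across five OSC settings.

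| Ions shifted | Q2 built once | Q2 nested | Difference | Across five settings |
|---|---|---|---|---|
| 10 by 1 SD | 0.25 | −0.37 | 0.62 | 0.18–0.76 |
| 10 by 2 SD | 0.44 | 0.06 | 0.38 | 0.18–0.41 |
| 40 by 2 SD | 0.81 | 0.70 | 0.11 | 0.08–0.21 |
| 40 by 4 SD | 0.95 | 0.92 | 0.03 | 0.02–0.06 |

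**7. Candidate list.** VIP comes from the final model, fitted to all 24 samples. Nesting alters only what happens inside the folds and permutations, so this model and its VIP values do not change. The t test is a separate step that does not use Q2.

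**The case against.** The strongest reply is that the SAP is silent rather than wrong. The order of its sentences is not an order of computation, and the model being validated may be meant to include its filter. This stands, so the point is conditional. A reader might infer that the SAP prescribes a fixed filter; the text does not say so. Naming the software does not settle it either way.

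The size rests on assumptions, and in four of the six settings in the first table the built-once Q2 is still negative and would not suggest predictive ability. That also stands: the direction is supported when ions are correlated, but no single figure is.

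A reader might infer that the permutation test is invalid in any case. It is not. Refitting the filter for each permutation brought rejection close to nominal even outside the folds, although Q2 itself stays biased there.

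A reader might also infer that the candidate list is contaminated. The documents do not support this, because neither measure gates selection and the final model is the same. It would be wrong, however, to defend the list by saying that OSC leaves VIP unchanged. That holds only for a one-component PLS model, and the SAP does not state the number. With two components, the largest VIP difference averaged 1.26, and only 28 of about 33 selected ions were in common.

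Finally, this is a discovery study whose candidates are only prioritised for identification. That limits the severity. It does not remove the point, since the SAP states no validation for the unfiltered models.

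**Conclusion.** The concern holds in conditional form. Run in the order described, without refitting, the pairwise OSC-PLS-DA for banana and for tomato would report a Q2 that is too high. If the filter also stays fixed to the true labels, the permutation test can reject too often.

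Without a food effect, the rise in Q2 ranges from negligible (0.03, uncorrelated ions) to about 1 (three iterative components), and fixed-filter rejection from nominal to over 90%. When the food effect is strong the distortion is small (0.02–0.06 for 40 ions shifted by 4 SD). These sizes rest on an assumed OSC algorithm, component number, ion correlation and ion count.

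The harm is limited to the reported Q2 and permutation result, and severity is minor to moderate. That the candidate list does not change assumes that component numbers are not themselves chosen by Q2; the SAP gives no rule for choosing them.

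**What to change.** Add to the SAP:

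- the OSC algorithm and the numbers of OSC and PLS components;
- scaling and OSC fitted on the training samples of each fold only, with the stored weights applied to the held-out samples;
- the whole sequence of scaling, OSC, PLS-DA and cross-validation repeated in each of the 500 permutations;
- because the data are paired, both samples of a subject kept in the same fold, and labels permuted within subject.

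Alternatively, report Q2 and the permutation test from an unfiltered pairwise PLS-DA validated in the same way, and use OSC-PLS-DA only to rank ions. The SAP explicitly names only a three-intervention PLS-DA, so the pairwise model would have to be stated. This route is valid but was less sensitive to weak effects in the simulation. Power of the permutation test, nested OSC against unfiltered, was 26% against 10% (10 ions, 1 SD), 79% against 21% (10 ions, 2 SD) and 100% against 95.5% (40 ions, 2 SD). Nesting is therefore preferable.

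The cost is a few sentences and a scripted loop, with no new data. The reported Q2 may be lower, but only if the filter would otherwise have been built once.
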